4.6.7 Electrocardiogram

4.6.7.1 Definitions and Derivations

The 12-lead ECGs will be recorded at visits specified in the CSP using an ECG machine that automatically calculates the heart rate and measures PR, QRS, QT, and QTcF intervals. Participants that were enrolled on CSP Version 1 (therefore with QTcB as an exclusion criterion at screening) should have both QTcB and QTcF collected at all timepoints throughout the study, and QTcF should be retrospectively calculated and reported for all visits that have previously occurred.

The rules described in Sections 3.3.1, 3.3.4, and 3.3.5 considering the definition of baseline, visit windows, and how to handle multiple records are followed.

The overall evaluation of an ECG is “normal,” “borderline,” or “abnormal,” with abnormalities categorised as either “clinically significant” or “not clinically significant.”

4.6.7.2 Presentations

A summary table of absolute values and change from baseline will be presented for each scheduled visit.

A frequency table showing the number of participants with their interpretation of the ECG reading (normal; borderline; abnormal, clinically not significant; abnormal, clinically significant) for each scheduled visit will be presented.

All ECG data will be listed, including a description of the abnormalities.

4.6.8 Echocardiogram

4.6.8.1 Definitions and Derivations

An ECHO to assess LVEF, end diastolic, and end systolic left ventricular volumes will be performed at visits specified in the CSP.

The rules described in Sections 3.3.1, 3.3.4, and 3.3.5 considering the definition of baseline, visit windows, and how to handle multiple records are followed.

4.6.8.2 Presentations

A summary table of absolute values and change from baseline of LVEF, end diastolic, and end systolic left ventricular volumes will be presented for each scheduled visit.

For ejection fraction decrease, a shift table showing CTCAE grades from baseline to maximum on-treatment will be produced.

All ECHO data will be listed.

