- The participant should be examined using the same machine and operator throughout the study wherever possible with a  $\pm$  7 day window for each assessment. If a participant has had an echocardiogram performed within 4 weeks prior to treatment discontinuation, the EoT visit echocardiogram scan is not required unless clinically indicated. An echocardiogram should be performed at the 30 day safety FU only in participants who have a drop in LVEF of  $\geq$  10 percentage points from baseline and to below the LLN at the time of selumetinib end of treatment visit, or if clinically indicated. Participants who have a drop in LVEF of >10 percentage points from baseline and to below the LLN at the time of selumetinib discontinuation should have a follow-up ECHO, ECG, vital signs and weight performed at 30 day safety follow-up.
- h. Assessment window  $\pm$  7 days. Ophthalmologic assessments may be performed more often, if clinically indicated, please see Appendix E 3 for more information. An ophthalmological examination should be performed at the 30 day safety FU only in participants with a retinal abnormality prior to or at time of end of treatment visit.
- i. Where feasible the knee MRI/X-ray will be performed at the same time as the PN volumetric MRI with a ± 7 day window for each assessment. Note that a wrist MRI/X-ray is acceptable if it is not possible to perform knee MRI/X-ray. The joint, which is imaged must be consistent throughout the study, except occasions where MRI/X-ray of the joint imaged at baseline is not possible.
- j Plexiform neurofibroma assessments will be performed at screening and every 4 cycles  $(16 \pm 1 \text{ weeks})$  for the first 13 cycles, and subsequently every 6 cycles  $(24 \pm 1 \text{ weeks})$ . MRI data for participants who discontinue selumetinib prior to C25 will be collected if a suitable MRI is performed as part of SoC until the time when they would have completed 25 cycles of treatment, or they commence an alternative systemic NF1-PN treatment, whichever is the

CCI									
	wice daily for Cycle 1	Week 1 and Cycle 7	Week 1 If	the assessment cannot	be done at Cycle 7	Week 1 then it sh	ould be performed	as soon as possible	

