- x. Adverse events will be collected from the time of signing the informed consent form, throughout the treatment period, and including the follow-up period.
- y. Other systemic NF1-PN targeted treatments will be collected for all participants who discontinue selumetinib until the time when they would have completed 25 cycles of treatment, or they commence an alternative systemic NF1-PN treatment whichever is the earliest.
- z. Consent can be performed on Day -42 onwards. All screening assessments must be performed within 28 days prior to dosing.

CCI	; BSA, body surface area; C, cycle; CSP, Clinical Study Protocol;
D, day; CCI	; ECG, electrocardiogram; EDC, electronic data capture; EoT, end of treatment; CC
CCI	; FU, follow-up; CCI
CCI	LLN, lower limit of normal; LVEF, left ventricular ejection fraction; MRI, magnetic resonance imaging; NF1, neurofibromatosis
type 1; PD, pharmacodynamic	: CC : PK, pharmacokinetic(s): PN, plexiform neurofibroma: SoC, standard of care;

VMI, Visual-Motor Integration; W, week.

AstraZeneca

	Participants receiving selumetinib treatment a			Participants no longer receiving selumetinib treatment		
Procedure b	Every 6 cycles	Every 12 cycles	EoT Safety Follow-up (30 days after last dose)	Every 6 months	Every year	Section or Appendix
Window	±7 days	±7 days	+ 7 days	± 7 days	±7 days	
Full Physical examination	Х		X	Х		8.3.1
Height, weight	Х		X	Х		8.3.2
BSA	Х			Х		8.3.2
Clinical safety laboratory assessments	Х		X	Х		8.3.9
12-lead ECG	Х		Х	If clinically	y indicated	8.3.4
Echocardiogram	Approximately	every 3 cycles	Х	If clinically indicated		8.3.5
Ophthalmology examination		X	Х	If clinically	y indicated	8.3.6
Knee MRI/X-ray (Physeal dysplasia)		X			Х	8.3.7
Performance status	Х		Х	Х		8.3.8
Urinalysis	Х		Х	Х		8.3.9
Vital signs	Х		Х	Х		8.3.3
CI	1	1				
Dispense medication d	To be dispensed	l every 2 cycles				6
Return Medication/Compliance Check		>	Х			6.2 6.4
SAEs and AEs causally related to selumetinib	←======	→	Х	← =======	→	8.4

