Potential risk of clinical significance	Rationale for risk	Mitigation strategy
Left ventricular ejection fraction decreases	Asymptomatic, Grade 1 or 2 LVEF decrease identified on routine ECHO are reported as very common ADRs in paediatric patients. Although symptomatic LVSD has not been reported in paediatrics, routine ECHO is important to detect any abnormality especially in very young patients for whom detection of symptoms (eg, dyspnoea, oedema, fatigue) may be more challenging.	Exclusion of participants with current unstable or uncompensated cardiac conditions or LVEF below LLN. See Appendix E for management guidelines.
Physeal dysplasia	Growth plate abnormalities have been seen in a single animal species at 11 times the clinical free exposure. This finding has also been reported preclinically with other MEK inhibitors. This preclinical risk has not been identified clinically following longitudinal assessment of height and growth velocity in paediatric patients on selumetinib (median total duration of exposure 28.1 months). However, there remains a potential risk of physeal dysplasia in paediatric patients with open growth plates, which could lead to joint pain and limb shortening. Routine monitoring during clinical studies is therefore required.	The healthcare professionals involved in clinical studies on paediatric populations should look for signs of physeal dysplasia (eg, joint pain and fatigue after exercising, abnormal gait, spine irregularities). Children who show signs of physeal dysplasia during treatment may need assessment of the knee or wrist joint by X-ray or MRI to assess for physical dysplasia. If clinical symptoms are identified at the time of selumetinib discontinuation participants should have a follow-up assessment after 30 days to evaluate the potential for reversibility.

ADR, adverse drug reaction; CPK, creatine phosphokinase; CSR, central serous retinopathy; ECHO, echocardiogram; IOP, intraocular pressure; LLN, lower limit of normal; LVEF, left ventricular ejection fraction; LVSD, left ventricular systolic dysfunction; MEK, mitogen activated protein kinase; MRI, magnetic resonance imaging; RPED, retinal pigment endothelial detachment; RVO, retinal vein occlusion; SAE, serious adverse event; SoA, schedule of activities.

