#### 8.3.5 **Echocardiogram**

An ECHO to assess LVEF will be performed at the visits as shown in the SoA. Participants should be examined using the same machine and operator whenever possible, and quantitative measurements should be taken (i.e., accurate to 1% and not estimated to 5%).

Left ventricular ejection fraction, end diastolic, and end systolic left ventricular volumes should be recorded at each ECHO assessment.

Participants experiencing an asymptomatic LVEF reduction or left ventricular systolic dysfunction should be managed according to the algorithm provided in Appendix E 1.

Participants who have a drop in LVEF of  $\geq 10$  percentage points from baseline and to below the LLN at the time of selumetinib discontinuation should, where possible, have follow-up ECHO, ECG, vital signs and weight performed after 30 days to evaluate the potential for reversibility.

An ECHO will also be carried out if a participant develops signs and/or symptoms suggestive of deterioration in left ventricular function/cardiac event.

A further ECHO should be performed as part of the assessment package for any cardiorespiratory AE with no obvious diagnosis (obvious causes will be managed in accordance with local clinical practice) and additionally at the discretion of the Investigator if clinically indicated.

If a participant has had an ECHO performed within 4 weeks prior to treatment discontinuation, the discontinuation visit ECHO scan is not required unless clinically indicated.

Concomitant cardiac symptoms should be reported as AEs/SAEs accordingly. Cardiac failure should be treated and followed according to local medical practice.

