3.3.4 Visit Window for safety and clinical outcome assessments

Visit windows will be defined for any presentations of safety and COAs that summarise values by visit. The following conventions will be applied:

- The time windows should be exhaustive so that data recorded at any timepoint have the potential to be summarised. Inclusion within the time window should be based on the actual date and not the intended date of the visit.
- All unscheduled visit data should have the potential to be included in the summaries.
- The window for the visits following baseline will be constructed in such a way that the upper limit of the interval falls halfway between the target days of the current and the next scheduled visit (the lower limit of the first post-baseline visit will be Day 2). If an even number of days exists between two consecutive visits, then the upper limit will be taken as the midpoint value minus 1 day. For example, the visit windows for vital signs data (with 2 weeks between scheduled assessments for Cycle 1 and 4 weeks for Cycle 2 onwards) are as follows:
 - Cycle 1 Day 15, visit window Days 2 to 21 –
 - Cycle 2 Day 1, visit window Days 22 to 42 –
 - Cycle 3 Day 1, visit window Days 43 to 70 –
 - Cycle 4 Day 1, visit window Days 71 to 98 –
 - etc.
- For summaries showing the maximum or minimum values, the maximum/minimum value recorded on treatment will be used (regardless of where it falls in an interval).
- Listings display all values contributing to a time point for a participant.
- For visit-based summaries, if there is more than one value per participant within a time window, then the closest value to the scheduled visit date will be summarised, or the earlier, in the event that the values are equidistant from the nominal visit date. The listings should highlight the value for the participant who contributed to the summary table, wherever feasible.

Note: In summaries of extreme values, all post-baseline values collected are used including those collected at unscheduled visits regardless of whether or not the value is close to the scheduled visit date.

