4.6 Safety Analyses

The domain “Safety” covers exposure, treatment compliance, AEs, clinical laboratory, vital signs, ECG, ECHO, ophthalmologic examinations, Knee/Wrist MRI/X-ray, performance status, **CCI** tests.

Safety data will be presented for all participants in the safety analysis set.

All planned data, including off-treatment data for participants who entered the long-term safety follow-up (participants < 5 years of age after 25 cycles of treatment or when they terminate treatment with selumetinib), will be presented in the listings for those assessments specified in the CSP Table 3.

Off-treatment data for participants who entered the long-term safety follow-up (participants < 5 years of age after 25 cycles of treatment or when they terminate treatment with selumetinib) will be presented separately in the summary tables and figures (if not otherwise specified) for those assessments specified in the CSP Table 3.

Off-treatment data will be included up until the first visit after the participant is \geq 5 years of age or they commence an alternative systemic NF1-PN targeted treatment, whichever is earlier.

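### The 30-day off-drug LVEF row would hold mainly children selected for a large fall, so partial recovery can print as a worse mean change from baseline

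*SAP*

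**What the plan says.** **Who is examined.** Protocol Table 2 marks ECHO at the 30-day safety follow-up, but footnote g restricts it: "An echocardiogram should be performed at the 30 day safety FU only in participants who have a drop in LVEF of" at least 10 percentage points from baseline and to below LLN at the end-of-treatment visit, or if clinically indicated. Protocol 8.3.5 gives the reason for this ECHO, which is to be "performed after 30 days to evaluate the potential for reversibility". On drug, ECHO follows a fixed schedule for every child. Table 2 also has an end-of-treatment ECHO, waived if one was done in the previous 4 weeks.

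**How it is summarised.** SAP 4.6.8.2, visit by visit: "A summary table of absolute values and change from baseline of LVEF, end diastolic, and end systolic left ventricular volumes will be presented". Baseline is the last value before first dose (SAP 3.3.1), missing values are not imputed (SAP 3.3.6), and on unscheduled data SAP 3.3.4 says: "All unscheduled visit data should have the potential to be included in the summaries". The LVEF shift table covers on-treatment values only.

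**Off-treatment data.** SAP 4.6 says that off-treatment data "will be presented separately in the summary tables and figures (if not otherwise specified) for those assessments specified in the CSP Table 3". That sentence is about children who entered the long-term safety follow-up. No separation is stated for the 30-day visit of other children.

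**Long-term follow-up.** In Table 3 the off-drug ECHO is done "If clinically indicated". The Table 3 column for 30 days after last dose, however, marks ECHO without any condition.

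**The concern.** A by-visit table of mean change from baseline is read down the rows as a time course. That reading is fair only if the same kind of children contribute to each row. At the Table 2 30-day visit the main entry rule is a large fall in LVEF, while the last on-drug ECHO covers all children still on schedule. A step down between these rows may reflect who was examined and not what happened after stopping.

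The protocol wants this examination in order to learn whether LVEF recovers. No planned summary compares a child's end-of-treatment value with the follow-up value, and the one table that would show the follow-up can point the wrong way.

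**Working it through.** The documents give no figure on this point, so there is none to reproduce. The direction follows from the rule; the size needs assumptions.

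**1. Bound from the rule alone.** Consider only children who meet footnote g. Each has a change of -10 or lower. If each regains a share r of the fall, their follow-up mean is at most -10 × (1 - r). This lies below an all-children mean of m whenever r < 1 - |m|/10. For assumed m of -1, -2 and -3, that means r below 0.90, 0.80 and 0.70.

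**2. Worked example (assumed values).** Twenty children have last on-drug changes of -14, -12 and eighteen of -1.
- Last on-drug mean: (-14 - 12 - 18)/20 = -44/20 = -2.2.
- Two children qualify and each regains half: -7 and -6.
- 30-day row: (-7 - 6)/2 = -6.5.
- Paired change in the same two children: (+7 + 6)/2 = +6.5.

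The row mean falls by 4.3 points while both children improve.

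**3. Simulation.** Assumptions, none from the documents except the entry floor of 55%: LLN 55; baseline LVEF mean 63 or 65, SD 4 or 5; on-drug change mean -1 to -3, SD 5 to 6; only rule-selected children examined.
- Share meeting the trigger: about 2% to 10%.
- On-drug mean change of those selected: -12.2 to -13.4, against -1 to -3 in all children.
- 30-day row: -9.1 to -10.1 at 25% recovery, -6.1 to -6.7 at 50%, -3.0 to -3.4 at 75%, and 0 at full recovery.
- The row looks worse than the last on-drug row unless recovery exceeds about 77% to 92%.

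**4. If other children are examined too.** Footnote g allows this where clinically indicated. Let p be the share selected, s their 30-day mean, T the 30-day mean in all children, and suppose 10% of the rest are examined. The rest have mean o = (T - p·s)/(1 - p), and the row is [p·s + 0.10(1 - p)·o]/[p + 0.10(1 - p)]. Both cases use 50% recovery, baseline mean 63 and SD 4.5.
- On-drug mean -2, SD 5 (p = 0.044, s = -6.2, T = -0.4): o = -0.13; row = (-0.273 - 0.013)/0.1396 = -2.0, equal to the end-of-treatment mean.
- On-drug mean -3, SD 6 (p = 0.101, s = -6.6, T = -0.9): o = -0.26; row = (-0.667 - 0.023)/0.1909 = -3.6, against -3.0.

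These T values let falls recover while rises persist. Halving every change instead gives T = -1.0 and -1.5, and rows of -2.5 and -3.9. The gap of about 4 points therefore shrinks to between 0 and 0.9.

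**The case against.** The other side is strong on scope and on consequence.

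- **Consequence.** Safety is descriptive only, and reversibility is not a listed objective. Continuous summaries print the number of observations, so a reader would see how few children contribute. All ECHO data are listed, and the LVEF shift table is unaffected. This stands, and it sets the priority.
- **Size.** Every LVEF figure above is assumed, and modest extra examination removes most or all of the effect. This stands.
- **Row structure.** The SAP does not say outright that the 30-day ECHO has its own row. I read it as a scheduled visit because Table 2 marks it. If the visit windows placed the value elsewhere, the selection would remain.

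A reader might also infer several stronger points, which the documents do not support:

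- *That all off-drug ECHO and eye examinations are confined to abnormal children.* Table 3 marks both without condition 30 days after last dose, and Table 2 schedules both at end of treatment.
- *That off-drug rows sit beside on-drug rows throughout.* SAP 4.6 separates them for long-term follow-up participants. The separation labels the data without removing the selection, but the tables are not side by side.
- *That eye results are biased in the same way.* The restriction exists: "An ophthalmological examination should be performed at the 30 day safety FU only in participants with a retinal abnormality". But fundoscopy is a frequency table that shows whether the examination was performed, and percentages default to the population total (SAP 3.3). Two abnormal of two examined among an assumed 36 treated prints as 2/36 = 5.6%, so the percentage is not inflated. Only intraocular pressure is shown as change from baseline, and it is not the trigger for re-examination.
- *That off-drug cardiac adverse event counts are misleadingly low.* Table 4 does say "Asymptomatic, Grade 1 or 2 LVEF decrease identified on routine ECHO are reported as very common ADRs in paediatric patients", and off-drug ECHO in long-term follow-up is not routine. But no comparison of on- and off-treatment event counts is planned, and collection in that phase is already narrower by design. No figure supports a share of events missed.

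**Conclusion.** The point holds for one summary: mean LVEF change from baseline at the Table 2 30-day follow-up. Entry to that row depends mainly on a prior fall, the comparison is with the pre-dose value, and the SAP has no rule for the selection. Partial recovery can therefore appear as a lower mean than at end of treatment. Given examination of selected children only, the direction is arithmetic unless recovery is near complete (above about 77% to 92% under the simulated values). The size is unknown and rests wholly on assumed LVEF distributions and recovery.

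The documents do not support extending this to ECG, to fundoscopy or to adverse event counts. It is a low-priority improvement that also answers the protocol's own question about reversibility.

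**What to change.** **SAP 4.6.8.2.** Leave the Table 2 30-day ECHO values out of the by-visit mean change-from-baseline summary. Add a small paired table of the children re-examined, giving:
- end-of-treatment value, follow-up value and within-child change;
- number examined over number who stopped;
- reason for the examination (met the LVEF rule, or clinically indicated).

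Treat clinically indicated off-drug ECHOs in long-term follow-up the same way, or list them only. Keep the Table 3 30-day ECHO values in the summaries, since that visit carries no condition.

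**Eye examinations.** At most, add a paired listing of retinal findings at end of treatment and at 30 days. The fundoscopy table can stay as it is.

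**Protocol.** The sponsor should reconcile the conditional footnotes of Table 2 with the unconditional marks in the 30-day column of Table 3. Footnote g also needs reconciling within itself: it gives the LVEF fall once as at least 10 percentage points and once as more than 10.

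**Cost.** SAP wording, one fewer summary row and one small extra table. No new examinations are needed.
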